### 7.1.1 Selected Adverse Events

The following TEAEs and related TEAEs will be summarized by SOC, preferred term, cohort, and treatment group:

- Dysgeusia
- Nausea
- Vomiting
- Diarrhea
- Neutropenia

These TEAEs and related TEAEs will also be summarized by PT by descending order of frequency.

### 7.2 Clinical Laboratory Data

Descriptive statistics for clinical laboratory values (in SI units) and changes from baseline at each assessment time point as well as shift tables from baseline to each visit for quantitative variables will be presented by cohort and treatment group for the following clinical laboratory variables (copy from the protocol).

**Hematology** Hemoglobin, hematocrit, red blood cells (RBC), platelet count, white blood cell count – total and differential (WBC), i.e. total neutrophils (absolute), eosinophils (absolute), monocytes (absolute), basophils(absolute), and lymphocytes (absolute).

**Biochemistry** Sodium, potassium, glucose(fasting), urea nitrogen, creatinine, calcium, chloride, thyroid stimulating hormone (TSH)a, thyroxine (free T4)triiodothyronine (T3), phosphate, protein, carbon dioxide, albumin, aspartate transaminase, alanine transaminase, gamma glutamyl transferase, alkaline phosphatase, total bilirubin, uric acid, and  $\beta$ -HCGa.

a Females only.

**Urinalysis** pH, glucose, protein, blood, ketones, bilirubin, nitrites, leukocyte esterase, and specific gravity.

Clinical laboratory test values are potentially clinically significant (PCS) if they meet either the low or high PCS criteria listed in [Table 1](#). The number and percentage of subjects with post-baseline PCS values will be tabulated by cohort and treatment group. The percentages will be calculated relative to the number of subjects with available baseline values and at least 1 post-baseline assessment. The numerator is the total number of subjects with at least 1 post-baseline

PCS value. A supportive listing of subjects with post-baseline PCS values will be provided including the subject number, baseline, and post-baseline values.

**Table 1 Criteria for Potentially Clinically Significant Laboratory Tests**

Parameter	Classification	Criteria: SI Units (Conventional Units)
Hematology		
Hemoglobin	High	>200 g/L (20g/dL)
	Low and Decrease	<100 g/L (10g/dL) AND Decrease of $\geq 20$ g/L (2.0 g/dL) from baseline value
Hematocrit	High	>1.3 $\times$ ULN
	Low and Decrease	$\leq 0.6 \times$ LLN AND Decrease of $\geq 6.0\%$ from baseline value
RBC	High	>7.5 $\times 10^{12}$ /L
	Low	<3.0 $\times 10^{12}$ /L
Platelets (thrombocytes)	High	>1.5 $\times$ ULN OR >500 $\times 10^9$ /L (500 $\times 10^3$ / $\mu$ L)
	Low	<0.6 $\times$ LLN OR <100 $\times 10^9$ /L (100 $\times 10^3$ / $\mu$ L)
WBC	High	>2 $\times$ ULN OR >16.0 $\times 10^9$ /L (16 $\times 10^3$ / $\mu$ L)
	Low	<0.5 $\times$ LLN OR <3.0 $\times 10^9$ /L (3 $\times 10^3$ / $\mu$ L)
Neutrophils	High	>6.2 $\times 10^9$ /L (6.2 $\times 10^3$ / $\mu$ L) OR > 70 %
	Low	<1.5 $\times 10^9$ /L (1.5 $\times 10^3$ / $\mu$ L) OR < 40%
Lymphocytes	High	> 4.0 $\times 10^9$ /L (4.0 $\times 10^3$ / $\mu$ L) OR > 44 %
	Low	<0.8 $\times 10^9$ /L (0.8 $\times 10^3$ / $\mu$ L) OR < 22 %
Monocytes	High	>1.1 $\times 10^9$ /L (1.1 $\times 10^3$ / $\mu$ L) OR >11 %
	Low	< 4 %
Eosinophils	High	>0.5 $\times 10^9$ /L (0.5 $\times 10^3$ / $\mu$ L) OR > 10.0%
	Low	NA
Basophils	High	>0.2 $\times 10^9$ /L (0.2 $\times 10^3$ / $\mu$ L) OR > 2%
	Low	NA
Biochemistry		
Sodium	High	>5 mmol/L (5 mEq/L) above ULN
	Low	>5 mmol/L (5 mEq/L) below LLN
Potassium	High and Increase	Above ULN AND Increase of > 0.5 mmol/L (0.5 mEq/L) from baseline value
	Low and Decrease	Below LLN AND Decrease of >0.5 mmol/L (0.5 mEq/L) from baseline value
Glucose (fasting)	High	$\geq 6.7$ mmol/L
	Low	$\leq 4.2$ mmol/L
BUN	High	>1.5 $\times$ ULN

**Table 1 Criteria for Potentially Clinically Significant Laboratory Tests**

Parameter	Classification	Criteria: SI Units (Conventional Units)
Creatinine	High and Increase	>150 µmol/L AND Increase > 30% from baseline value
	Low and Decrease	NA
Calcium	High and Increase	Above ULN AND Increase of ≥ 0.25 mmol/L (1.0 mg/dL) from baseline value
	Low and Decrease	Below LLN AND Decrease of ≥0.25 mmol/L (1.0 mg/dL) from baseline value
Carbon dioxide (Total)	High	>32 mmol/l (mEq/l)
	Low	< 20 mmol/l (mEq/l))
Phosphate	High	>0.162 mmol/L (0.5 mg/dL) above ULN
	Low	>0.162 mmol/L (0.5 mg/dL) belowLLN
Chloride	High	>110 mmol/L (>110 mEq/L)
	Low	<98 mmol /L (<98 mEq/L)
Protein (Total)	High and Increase	Above ULN AND Increase of ≥20 g/L (2.0 g/dL) from baseline value
	Low and Decrease	Below LLN AND Decrease of ≥20 g/L (2.0 g/dL) from baseline value
Albumin	High and Increase	Above ULN AND Increase of ≥10 g/L (1.0 g/dL) from baseline value
	Low and Decrease	Below LLN AND Decrease of ≥10 g/L (1.0 g/dL) from baseline value
Aspartate transaminase	High	>2 × ULN
Alanine transaminase (ALT)	High	>2 × ULN
Gamma glutamyl transferase (GGT)	High	>1.5 × ULN
Alkaline phosphatase (ALP)	High	>1.5 × ULN
Total bilirubin	High and Increase	>1.5 × ULN
Uric acid (with normal diet)	High and Increase	Above ULN AND Increase of >0.119 mmol/L (2.0 mg/dL) from baseline value
	Low and Decrease	Below LLN AND Decrease of >0.119 mmol/L (2.0 mg/dL) from baseline value
Thyroid stimulating hormone (TSH)	High	>5.0 µU/L (>5.0 µU/mL)
	Low	<0.5 µU/L (<0.5 µU/mL)

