4.1 Inclusion Criteria

The screening period starts with the signing of the informed consent. During the screening period, inclusion/exclusion criteria for study participation will be checked/tested. The subject will not be considered eligible for the study without meeting all of the criteria below.

Subjects cannot be enrolled or randomized before all inclusion criteria (including test results) are confirmed.

1. An understanding, ability, and willingness to fully comply with study procedures and restrictions.
2. Ability to voluntarily provide written, signed, and dated (personally or via a legally-authorized representative) informed consent/assent as applicable to participate in the study.
3. Healthy subjects of Japanese descent must have been born in Japan and must not have lived outside of Japan for >10 years; both parents and all 4 grandparents must be of Japanese origin. Healthy, non-Hispanic, Caucasian subjects must have both parents and all 4 grandparents of non-Hispanic, Caucasian origin.
4. Age 18 to 55 years inclusive, at the time of consent. The date of signature of the informed consent is defined as the beginning of the screening period. This inclusion criterion will only be assessed at the first screening visit.
5. Male, or non-pregnant, non-breastfeeding female who agrees to comply with any applicable contraceptive requirements of the protocol or females of non-childbearing potential.
6. Healthy as determined by the investigator on the basis of screening evaluations. Healthy status is defined by absence of evidence of any active or chronic disease following a detailed medical and surgical history, a complete physical examination including vital signs, 12-lead ECG, hematology, blood chemistry (includes thyroid stimulating hormone [TSH] and free T4 at screening only), and urinalysis.
7. Hemoglobin for males ≥ 135.0 g/L and females ≥ 120.0 g/L at screening and on Day -1.
8. BMI between 18.5 and 28.0 kg/m² inclusive with a body weight >45 kg (99 lbs.). This inclusion criterion will only be assessed at the first screening visit.
9. Ability to swallow a dose of IP.

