**Table 1 Criteria for Potentially Clinically Significant Laboratory Tests**

Parameter	Classification	Criteria: SI Units (Conventional Units)
Thyroxine (free T4)	High	> 24.54 pmol/L (>1.9 ng/dL)
	Low	< 9.01 pmol/ L (<0.7 ng/dL)
Triiodothyronine (T3) Total	High	>2.78 nmol/L (<181 ng/dL)
	Low	<0.92 nmol/L (<60ng/dL)
Urinalysis		
Glucose	High	≥1+
Protein	High	≥2+
Blood	High	≥2+
Ketones	High	≥2+
Bilirubin	Abnormal	Positive
Nitrites	Abnormal	Positive
Leukocyte esterase	Abnormal	Positive

BUN=Blood Urea Nitrogen, LLN=lower limit of normal value provided by the laboratory, RBC=Red Blood Cells, ULN=upper limit of normal value provided by the laboratory, WBC=White Blood Cells.

All laboratory data will be listed for the Safety Set.

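### SAP Table 1 sets the SI limits for TSH 1000 times too low and reverses the bracketed T3 sign; separately, a footnote confines TSH to females although inclusion criterion 6 does not.

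*SAP*

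**What the plan says.** **Limits.** The criteria column of SAP Table 1 gives an SI limit first and the conventional equivalent in brackets. The thyroid rows relevant here are:

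- TSH high: ">5.0 µU/L (>5.0 µU/mL"
- TSH low: "<0.5 µU/L (<0.5 µU/mL"
- Total T3 high: ">2.78 nmol/L (<181 ng/dL"
- Total T3 low: "<0.92 nmol/L (<60ng/dL"

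**Use of the limits.** SAP 7.2 sets the unit system ("Descriptive statistics for clinical laboratory values (in SI units") and asks for changes from baseline and shift tables. It applies the Table 1 limits after dosing: "The number and percentage of subjects with post-baseline PCS values will be tabulated by cohort and treatment group". The denominator is subjects with a baseline value and at least one post-baseline assessment. Protocol 8.8 leaves the definition of potentially clinically important values to the SAP, so Table 1 governs.

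**Who is tested, and when.** Inclusion criterion 6 (protocol synopsis and 4.1) defines healthy status from screening results that include "blood chemistry (includes thyroid stimulating hormone [TSH] and free T4 at screening only", with no restriction by sex. The biochemistry lists in protocol 7.2.2.6 and SAP 7.2 contain TSH, free T4 and T3 with no restriction by visit. Both lists attach to TSH the same females-only footnote that they attach to β-HCG.

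**The concern.** The two halves of a limit in Table 1 should say the same thing. For TSH they differ by a factor of 1000, and for T3 high they point in opposite directions. A programmer has to guess which half to code. If the SI half of the TSH rule is coded as printed, the tabulation of potentially clinically significant (PCS) values would show close to 100% high TSH in both cohorts and at every dose, and could not show a low value. Safety and tolerability are secondary objectives, and the 400 mg safety data are to be compared directly between the cohorts, so an uninformative row in that table is worth preventing.

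The footnote is a different kind of problem. The study may enrol men. Protocol 4.1 forbids enrolment until all inclusion criteria, including test results, are confirmed. Read literally, the footnote leaves men without one of the results that criterion 6 names.

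**Working it through.** **Inputs.** All limits come from SAP Table 1. The unit system and the use of the flags come from SAP 7.2. The only outside fact is that 1 L = 1000 mL.

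**1. TSH.**

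- High limit: 5.0 µU/mL × 1000 = 5000 µU/L = 5.0 mU/L. Printed: 5.0 µU/L. Ratio 5000/5.0 = 1000.
- Low limit: 0.5 µU/mL × 1000 = 500 µU/L = 0.5 mU/L. Printed: 0.5 µU/L. Ratio 500/0.5 = 1000.
- Converted back, the printed SI limits are 5.0/1000 = 0.005 µU/mL (high) and 0.5/1000 = 0.0005 µU/mL (low).

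The printed equivalence is therefore not reproduced. Changing the SI unit to mU/L makes both pairs agree with no change to any number. Applying each half of the rule to illustrative values gives:

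| TSH (µU/mL) | TSH (µU/L) | SI limits as printed | Conventional limits |
|---|---|---|---|
| 0.3 | 300 | High | Low |
| 0.5 | 500 | High | none |
| 1 | 1000 | High | none |
| 2.5 | 2500 | High | none |
| 5 | 5000 | High | none |
| 8 | 8000 | High | High |

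The SI rule flags all six as high and none as low, including the value that the conventional rule calls low.

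**2. T3.** The table's own conversion factor is 60/0.92 = 65.2 ng/dL per nmol/L from the low row and 181/2.78 = 65.1 from the high row. As a check, 0.92/60 × 181 = 2.78 nmol/L. The numbers agree, so only the sign in the bracket is wrong.

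| T3 (ng/dL) | T3 (nmol/L) | SI high rule (>2.78) | Bracketed high rule (<181) | Low rule (<60 ng/dL) |
|---|---|---|---|---|
| 40 | 0.61 | no | yes | yes |
| 100 | 1.53 | no | yes | no |
| 150 | 2.30 | no | yes | no |
| 200 | 3.07 | yes | no | no |

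The SI rule behaves as intended. The bracketed rule would call 40 ng/dL both high and low, and would miss 200 ng/dL.

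**3. Footnote against criterion 6.** Criterion 6 has TSH for every subject at screening. The footnote in protocol 7.2.2.6, repeated in SAP 7.2, has TSH for females only. Free T4, named beside TSH in criterion 6, carries no footnote. Both statements cannot be followed for a male subject.

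**4. Timing.** Criterion 6 puts TSH and free T4 at screening only and does not mention T3. The panel lists carry no such limit, and protocol Tables 1 and 5 schedule biochemistry at screening, on Day -1, on Days 1 and 2, and at early termination. Either TSH and free T4 are measured after dosing, in which case the TSH limit matters, or they are not, in which case SAP 7.2 specifies change, shift and PCS tables that have no data.

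**The case against.** The strongest objection is that a post-dose TSH is not established. Criterion 6 says screening only, and presence on the panel list proves little: β-HCG is on the same list, yet protocol Tables 1 and 5 place the serum test only at screening and Day -1. If TSH is screening-only, nobody enters the PCS denominator and no flag can misfire. This stands, and it makes the TSH consequence conditional. It does not remove the error in the table, and it exposes the second inconsistency, that the SAP plans post-baseline outputs for a test that may not be done then.

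It is also fair to say that a sensible programmer would probably avoid the trap. If the laboratory reports TSH in mU/L or µU/mL and the number 5.0 is used directly, the flag works. All laboratory data are listed, so the actual values stay visible whatever the flags show.

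A reader might infer three stronger things, which the documents do not support.

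- *That the unit and sign errors affect who is enrolled.* They cannot. Table 1 is applied to post-baseline values. Healthy status is the investigator's judgement on screening results, and protocol 7.2.2.6 has results assessed against the laboratory's reference ranges.
- *That the T3 and TSH flags would both fail.* No single unit system produces both. In SI units the T3 rule is right and the TSH rule wrong. In conventional units it is the reverse.
- *That the free T4 high limit ("> 24.54 pmol/L (>1.9 ng/dL") is also wrong.* Its ratio is 24.54/1.9 = 12.92 against 9.01/0.7 = 12.87 in the low row. The low-row ratio would give 12.87 × 1.9 = 24.46 pmol/L, a gap of about 0.3%. The documents give no conversion factor, so they cannot show which row is off, and the gap has no practical effect.

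On the footnote, a site that follows criterion 6 would test everyone. What is shown is a conflict of wording, not an eligibility failure that has occurred.

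**Conclusion.** Three defects hold as written.

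- Both SI limits for TSH are too low by exactly 1000. If TSH is measured after baseline and the printed SI limit is applied, essentially every value is flagged high and none low. Both conditions are assumptions. The documents contradict themselves on the first, and SAP 7.2 points to the second.
- The bracketed T3 high criterion has a reversed sign. Its SI criterion is correct, so the flag fails only if the conventional half is coded.
- The females-only footnote on TSH contradicts inclusion criterion 6 in both documents. This is the only one of the three that touches eligibility, and it does so as a missing test in men if the footnote is followed.

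The importance is low. There is no effect on the primary comparison of Cmax, AUClast and AUC0-inf, on dose proportionality or on the sample size. The correction is nearly free and should be made before the safety tables are programmed.

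**What to change.** 1. In SAP Table 1, write the TSH limits as >5.0 mU/L (>5.0 µU/mL) and <0.5 mU/L (<0.5 µU/mL).
2. In the T3 high row, change the bracket to >181 ng/dL and leave the SI limit as it is.
3. Reconcile the females-only footnote on TSH with inclusion criterion 6, in protocol 7.2.2.6 and in SAP 7.2, so that both documents state the same testing rule.
4. State for each of TSH, free T4 and T3 at which visits it is measured. Reconcile the screening-only wording of criterion 6 with the panel lists for TSH and free T4, and state the timing of T3, which that wording does not cover. Remove any test that is screening-only from the post-baseline change, shift and PCS tables.

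The cost is a few words in one SAP table and section, and a correction to one protocol footnote and panel list. No analysis method changes.

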**Table 1 Criteria for Potentially Clinically Significant Laboratory Tests**

Parameter	Classification	Criteria: SI Units (Conventional Units)
Thyroxine (free T4)	High	> 24.54 pmol/L (>1.9 ng/dL)
	Low	< 9.01 pmol/ L (<0.7 ng/dL)
Triiodothyronine (T3) Total	High	>2.78 nmol/L (<181 ng/dL)
	Low	<0.92 nmol/L (<60ng/dL)
Urinalysis		
Glucose	High	≥1+
Protein	High	≥2+
Blood	High	≥2+
Ketones	High	≥2+
Bilirubin	Abnormal	Positive
Nitrites	Abnormal	Positive
Leukocyte esterase	Abnormal	Positive

BUN=Blood Urea Nitrogen, LLN=lower limit of normal value provided by the laboratory, RBC=Red Blood Cells, ULN=upper limit of normal value provided by the laboratory, WBC=White Blood Cells.

All laboratory data will be listed for the Safety Set.

### 7.3 Vital Signs

Descriptive statistics for vital signs (e.g., systolic and diastolic blood pressure, pulse rate, body temperature, respiratory rate, and body weight) and their changes from baseline at each post-baseline visit and at the end of study will be presented by cohort and treatment group.

Vital sign values will be considered PCS if they meet both the observed value criteria and the change from baseline criteria listed in Table 2. The number and percentage of subjects with PCS post-baseline values will be tabulated by cohort and treatment group. The percentages will be calculated relative to the number of subjects with baseline and at least 1 post-baseline assessment. The numerator is the total number of subjects with at least 1 PCS post-baseline vital sign value. A supportive listing of subjects with post-baseline PCS values will be provided including the subject number, baseline, and post-baseline PCS values.

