7.2.2.6 Clinical Laboratory Tests

The name and address of each third party vendor (eg, clinical laboratory) used in this study will be maintained in the investigator's and sponsor's files.

All clinical laboratory tests will be performed according to the laboratory's standard procedures.

The subject should not eat or drink anything for at least 8 hours to 10 hours before having clinical laboratory tests.

Reference ranges will be supplied by the laboratory and used to assess the results for clinical significance and out-of-range changes which may be associated with, or constitute, an AE. The investigator should assess out-of-range clinical laboratory values for clinical significance, indicating if the value(s) is/are not clinically significant or clinically significant. Abnormal clinical laboratory values, which are unexpected or not explained by the subject's clinical condition, may, at the discretion of the investigator or sponsor, be repeated as soon as possible until confirmed, explained, or resolved.

The following clinical laboratory assessments will be performed:

Biochemistry

Blood samples for serum biochemistry will be collected into a serum separator tube at the time points described in [Table 1](#), [Table 2](#), [Table 3](#), [Table 4](#), [Table 5](#), and [Table 6](#). The following parameters will be assessed:

Sodium	Phosphate	β -HCG ^a
Potassium	Protein	
Glucose(fasting)	Carbon dioxide	
Urea nitrogen	Albumin	
Creatinine	Aspartate transaminase	
Calcium	Alanine transaminase	
Chloride	Gamma glutamyl transferase	
Thyroid stimulating hormone (TSH) ^a	Alkaline phosphatase	
Thyroxine (free T4)	Total bilirubin	
Triiodothyronine (T3)	Uric acid	

^a Females only.

Hematology

Blood samples for hematology will be collected into a K₂EDTA tube at the time points described in [Table 1](#), [Table 2](#), [Table 3](#), [Table 4](#), [Table 5](#), and [Table 6](#). The following parameters will be assessed:

Hemoglobin	Total neutrophils (absolute)
Hematocrit	Eosinophils (absolute)
Red blood cells	Monocytes (absolute)
Platelet count	Basophils (absolute)
White blood cell count; total and differential	Lymphocytes (absolute)

Urinalysis

A urine sample for urinalysis will be collected at the time points described in [Table 1](#), [Table 2](#), [Table 3](#), [Table 4](#), [Table 5](#), and [Table 6](#). The following parameters will be assessed:

pH	Blood	Nitrites
Glucose	Ketones	Leukocyte esterase
Protein	Bilirubin	Specific gravity

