**Table 2 Criteria for Potentially Clinically Significant Vital Signs and Body Weight**

Vital Sign Parameter	Flag	Criteria a	
		Observed Value	Change from Baseline Value
Systolic blood pressure (mmHg)	High	≥140	Increase of ≥20
	Low	≤90	Decrease of ≥20
Diastolic blood pressure (mmHg)	High	≥90	Increase of ≥15
	Low	≤50	Decrease of ≥15
Heart rate	High	≥100	Increase of ≥15

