**Table 2 Criteria for Potentially Clinically Significant Vital Signs and Body Weight**

Vital Sign Parameter	Flag	Criteria a	
		Observed Value	Change from Baseline Value
(beats per minute)	Low	≤45	Decrease of ≥15
Weight (kg)	High	-	Increase of ≥5%
	Low	-	Decrease of ≥5%
Body temperature	High	> 38.3°C or > 100.9°F	
	Low	< 35°C or < 95°F	
Respiratory rate (breaths/min)	High	> 25	
	Low	< 10	

a A post-baseline value is considered as a PCI value if its meets both criteria for observed value and change from baseline. All vital signs data will be listed for the Safety Set.

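### The vital-sign PCS rule demands two criteria, but Table 2 gives only one for weight, temperature and respiratory rate, so 6 of its 12 rows cannot be flagged as written

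*SAP*

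**What the plan says.** Protocol 8.8 leaves the definition of potentially clinically important values to the SAP. SAP 7.3 supplies it for vital signs: "Vital sign values will be considered PCS if they meet both the observed value criteria and the change from baseline criteria listed in Table 2". Footnote a of Table 2 states the same condition for the whole table: "A post-baseline value is considered as a PCI value if its meets both criteria for observed value and change from baseline".

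Table 2 has six parameters, each with a High and a Low row. Systolic pressure, diastolic pressure and heart rate have entries in both columns. For weight, the observed-value column holds a dash and only the change column is filled ("Increase of ≥5" percent for High). For body temperature only the observed-value column is filled ("> 38.3°C or > 100.9°F" for High), and respiratory rate is laid out in the same way. Neither SAP 7.3 nor the footnote says how to treat a row with one criterion.

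The rule drives two outputs: a table of the number and percentage of subjects with a post-baseline PCS value, by cohort and treatment group, and a supporting listing of those subjects.

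**The concern.** A condition that needs two criteria cannot be satisfied where the table supplies one. If the text is programmed as it stands, the weight, temperature and respiratory-rate rows show zero subjects whatever the data are. Someone reading the report could not tell that structural zero from a true absence of such values.

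Safety and tolerability at each dose are secondary objectives, and Protocol 8.8 plans a direct comparison of the two cohorts at 400 mg. The PCS table is one of the displays a reader would use for that. If the programmer instead supplies a rule for single-criterion rows, the result is probably what was meant, but it rests on a decision that is not in the plan.

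**Working it through.** The SAP gives no computed figure on this point, so there is nothing to reproduce. The check is a count of rows against the rule.

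**Inputs.** The rule comes from SAP 7.3 and Table 2 footnote a; the entries come from SAP Table 2.

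| Parameter | Rows | Observed-value criterion | Change criterion | Both present? |
|---|---|---|---|---|
| Systolic pressure | 2 | ≥140 / ≤90 | ≥20 | yes |
| Diastolic pressure | 2 | ≥90 / ≤50 | ≥15 | yes |
| Heart rate | 2 | ≥100 / ≤45 | ≥15 | yes |
| Weight | 2 | dash | ≥5% | no |
| Body temperature | 2 | >38.3 °C / <35 °C | none | no |
| Respiratory rate | 2 | >25 / <10 | none | no |

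**Count.** Total rows: 6 parameters × 2 = 12. Rows lacking one required criterion: 2 (weight) + 2 (temperature) + 2 (respiratory rate) = 6. Rows that can be flagged under the literal rule: 12 − 6 = 6.

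**Examples under the literal rule.**
- Temperature 39.5 °C: the observed value passes (39.5 > 38.3). There is no change criterion to meet, so both are not met and the value is not PCS.
- Respiratory rate 30: the observed value passes (30 > 25). There is no change criterion, so it is not PCS.
- Weight change of exactly 5%: the change passes. There is no observed-value criterion, so it is not PCS.

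**Under a rule that applies every criterion given for the row.** All 12 rows can be flagged, 6 on two criteria and 6 on one. All three examples become PCS.

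**Comparison with the other PCS tables.** SAP Table 1 (laboratory) and Table 3 (ECG) also mix single and compound criteria, for example QRS against PR interval. There, any joint condition is written inside the row, and the governing text does not require two columns to be met. The conflict is therefore particular to Table 2.

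**Size of one missed subject.** With 12 subjects in a cohort, all with baseline and post-baseline values, one subject wrongly left out lowers the tabulated percentage by 1/12 = 8.3 points.

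**The case against.** The strongest reply is that nobody writes numeric limits for rows that are meant never to fire. SAP 7.3 refers to the criteria listed in Table 2, so an unlisted criterion is naturally read as not required. The specifications for tables, figures and listings are in a separate document (SAP 1) and may settle the matter. This is a fair account of the likely intent, and the dash for weight supports it. It does not remove the conflict: the footnote repeats the two-criterion rule with no exception, and the SAP is where the protocol says the definition will be found.

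A reader might infer that the trial is blind to fever, respiratory rate or weight change. The documents do not support that. SAP 7.3 summarises all three with changes from baseline by cohort and treatment group. All vital-sign data are listed for the Safety Set. Protocol Appendix 2.1 lets a clinically relevant vital-sign change be recorded as an adverse event. A temperature of 39.5 °C would be seen; it would be missing only from the PCS table and PCS listing.

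A reader might also infer that the PCS rules fail in the opposite direction for the white-cell differential, because Table 1 joins an absolute and a percentage limit with OR. The arithmetic behind this is right. The two limits agree only at WBC = absolute limit / percentage limit: for low neutrophils 1.5/0.40 = 3.75 ×10⁹/L, and for low lymphocytes 0.8/0.22 = 3.64. At WBC 7.0, 38% neutrophils is 7.0 × 0.38 = 2.66, above the 1.5 limit, yet flagged low. That does not make it an error. The OR is explicit and can be programmed, the table uses the same structure for platelets and WBC, and a broad screen for potential significance is a defensible choice. The documents give no WBC or differential distribution, so the rate of extra flags cannot be derived from them. Removing the percentage limits would be a preference about thresholds, and would leave low monocytes with no criterion at all.

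**Conclusion.** The vital-sign rule is wrong as written: SAP 7.3 and footnote a contradict Table 2 for 6 of its 12 rows. The defect is minor. It affects one descriptive PCS table and its listing in a planned 24 subjects, and leaves the vital-sign summaries, the full listings, adverse-event reporting and the primary PK analysis unchanged.

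The count of 6 rests on the literal reading, and on the empty change cells for temperature and respiratory rate being as the sponsor intended. If entries for those four rows have been lost from the table, the conflict shrinks to the two weight rows, where the dash is explicit. If the programmer treats an empty cell as no requirement, the output will be sensible but will follow an unwritten rule.

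The percentage limits in Table 1 call for no more than a query to the sponsor.

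**What to change.** Replace the condition in SAP 7.3 and in Table 2 footnote a with:

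> A value is PCS if it meets every criterion given for its row of Table 2; where only one criterion is given, that criterion alone applies.

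Use the same term in both places, since the text says PCS and the footnote PCI. Check that the table and listing specifications follow the sentence. No limit changes and no new data are needed. The cost is a short SAP amendment before database lock.

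Separately, ask the sponsor to confirm that the percentage limits joined by OR in Table 1 are intended, since they can flag counts inside the table's own absolute limits. No edit to Table 1 is proposed.
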